		Cycle 1				Cycles 2-4		Cycle 5			Cycles 8, 12, 16, 20, 24	EOT	Follow Up ^[32]
Visit Window Cycle 1(+2 days Cycles 2–5: (±) 2 days Cycles >5: (±) 7 days	(≤28 days of registration	Day 1	Day 8	Day 15	Day 22	Day 1	Day 1	Day 8	Day 15	Day 1			
Blood for PF-05082566 PK ^[21]		X				X	X	X	X	X	X	X	
Blood for Mogamulizumab PK ^[22]		X	X	X	X	X	X	X	X	X	X	X	
CCI													
Banked Biospecimen (DNA) ^[23]		X											
Blood for Pharmacogenomics (RNA) ^[26]		X				X (C 2 & 3 only)	X				X		
Blood for PF-05082566 Immunogenicity testing ^[27]		X				X (C3 only)	X			X	X	X	
Blood for Mogamulizumab Immunogenicity testing ^[28]		X				X (C3 only)	X			X	X	X	
CCI													

Footnotes for Schedules of Activities	
1. Screening:	To be obtained within 28 days prior to registration.
2. Informed Consent:	Must be obtained prior to undergoing any study specific procedure and may occur prior to the 28-day screening period.
3. Tumor History:	Includes oncology history; information on prior regimens (including dosing and duration of administration, description of best response observed, recurrence date), surgery and radiation therapy.
4. Medical History:	Includes history of other diseases (active or resolved) and concomitant illnesses.
5. Physical Examination:	Includes an examination of major body systems. Weight for the purposes of dose calculation will be recorded at screening and within 7 days pre-dose Day 1 of each cycle. Weight will not be collected at End of Treatment. Height will be measured at baseline only.
6. ECOG PS:	ECOG performance scale is available as Appendix 1 .
7. Vital Signs:	blood pressure (BP) and pulse rate to be recorded in supine or sitting position.
8. Hematology:	No need to repeat on C1D1 if baseline assessment performed within 7 days prior to that date. On treatment, to be performed prior to dosing with study medications unless otherwise indicated. If during the first 2 cycles of treatment a Grade 4 hematologic event is evident, the hematology assessment should be repeated at least every other day to assess for events qualifying as DLT. See Table 10 in Section 7.1.3 , Laboratory Safety Assessments, for the list of the required Laboratory Tests.

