14. Thyroid and other Endocrine Function Tests :	On treatment, thyroid function tests will be performed in cases of clinical symptoms consistent with thyroiditis. On treatment, other endocrine function tests (in addition to T3, FT4, and TSH) will be performed in cases of suspected hypoadrenalinism or hypopituitarism See Table 10 , in Section 7.1.3 , Laboratory Safety Assessments, for the list of the required Laboratory Tests.
15. Registration:	Patient number and dose level allocation operated by Pfizer Inc. Study treatments administration should begin within 7 days of registration.
16. PF-05082566 Administration:	Treatment will be administered in a 4-week cycle (ie, 28-day cycle). PF-05082566 will be administered as a 1-hour IV infusion on Day 1 of each cycle. When both PF-05082566-and mogamulizumab are administered, PF-05082566 will be administered first. Treatment will continue until completion of 24 months of treatment (approximately 24 cycles), or for one of the reasons listed for patient withdrawal as specified in Section 6.4 .

17. **Mogamulizumab Administration:** Treatment will be administered in a 4-week cycle (ie, 28-day cycle). In Cycle 1, Mogamulizumab will be administered as a 1-hour IV infusion every week (ie, on Days 1, 8, 15, 22). From Cycle 2 onwards, mogamulizumab will be administered every 2 weeks (ie, on Days 1 and 15 of every cycle). On Day 1, mogamulizumab infusion will start 30 minutes (\pm 10 min) after completion of PF-05082566 infusion and after the post-PF-05082566 and pre-mogamulizumab pharmacokinetic blood samples are drawn. Treatment will continue until completion of 24 months of treatment (approximately 24 cycles), or for one of the reasons listed for patient withdrawal as specified in [Section 6.4](#).

18. **Tumor Assessments:** Assessment of response will be made using RECIST version 1.1 and irRC (see [Appendix 2](#) and [Appendix 3](#) for details). Antitumor activity will be assessed through radiological tumor assessments conducted at baseline, on treatment every 8 weeks up to 1 year, then every 3 months and whenever disease progression is suspected (eg, symptomatic deterioration). To be repeated at EOT only if not done in the previous 8 weeks. Confirmation of response (CR/PR) should be done at least 4 weeks after the initial response. Timing should follow calendar days and should not be adjusted for delays in cycle starts. (See [Section 7.2](#) for further details).

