5.4. Administration

Study treatment administration should start no later than 7 days after registration.

A cycle is defined as the time from Day 1 dose to the next Day 1 dose of PF-05082566. If there are no treatment delays, a cycle will be 4 weeks in duration.

All trial treatments will be administered on an outpatient basis. After Cycle 1, study drugs may be administered up to 2 days before or after the scheduled treatment day of each cycle for administrative reasons. Patients will be observed in the clinic for at least 2 hours after the administration of study drug, throughout the duration of the study.

All patients should be weighed within 7 days prior to dosing for every cycle to ensure they did not experience either a weight loss or gain >10% from the prior weight used to calculate the amount of study drug required for dose preparation. Decision to recalculate the study drug dose based on the weight obtained at each cycle can be in accordance with institutional practice, however if the patient experienced either a weight loss or gain >10% compared to the weight used to calculate the initial dose, the amount of study drug required for preparation and administration for the current cycle must be recalculated using this most recent weight obtained.

As with any antibody, allergic reactions to dose administration are possible. Therefore, appropriate drugs and medical equipment to treat allergic or anaphylactic reactions must be immediately available, and study personnel must be trained to recognize and treat allergic and anaphylactic reactions. Patients should be instructed to report any delayed reactions to the Investigator immediately. If a patient experiences an infusion related reaction at any time during the study, premedication is recommended prior to subsequent infusions (see Section 5.4.2 for details on premedication to be used).

For both drugs, the exact duration of infusion should be recorded in both sources document and CRFs. The infusion rate should be reduced or interrupted in the case of symptoms of infusion reaction, and symptomatic treatment administered. The infusion may be continued at one-half the previous rate upon improvement of symptoms. If symptoms persist or worsen, the infusion should be discontinued.

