6.1. Screening

For screening procedures, see [Schedule of Activities](#) and [ASSESSMENTS](#) Sections.

Screening is to be performed within 28 days of registration. Tumor history includes information on prior regimens (including dosing and duration of administration, description of best response observed, recurrence date), surgery and radiation therapy. Medical history, includes history of other diseases (active or resolved) and concomitant illnesses.

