All sites of disease must be assessed at baseline. Baseline assessments should be done as close as possible prior to study start. For an adequate baseline assessment, all required scans must be done within 28 days prior to treatment and all disease must be documented appropriately. If baseline assessment is inadequate, subsequent statuses generally should be indeterminate.

Target lesions

All measurable lesions up to a maximum of 2 lesions per organ, 5 lesions in total, representative of all involved organs, should be identified as target lesions at baseline. Target lesions should be selected on the basis of size (longest lesions) and suitability for accurate repeated measurements. Record the longest diameter for each lesion, except in the case of pathological lymph nodes for which the short axis should be recorded. The sum of the diameters (longest for non-nodal lesions, short axis for nodal lesions) for all target lesions at baseline will be the basis for comparison to assessments performed on study.

If two target lesions coalesce the measurement of the coalesced mass is used. If a large target lesion splits, the sum of the parts is used.

Measurements for target lesions that become small should continue to be recorded. If a target lesion becomes too small to measure, 0 mm should be recorded if the lesion is considered to have disappeared; otherwise a default value of 5 mm should be recorded.

NOTE: When nodal lesions decrease to <10 mm (normal), the actual measurement should still be recorded.

Non-target disease

All non-measurable disease is non-target. All measurable lesions not identified as target lesions are also included as non-target disease. Measurements are not required but rather assessments will be expressed as ABSENT, INDETERMINATE, PRESENT/NOT INCREASED, INCREASED. Multiple non-target lesions in one organ may be recorded as a single item on the case report form (eg, 'multiple enlarged pelvic lymph nodes' or 'multiple liver metastases').

OBJECTIVE RESPONSE STATUS AT EACH EVALUATION

Disease sites must be assessed using the same technique as baseline, including consistent administration of contrast and timing of scanning. If a change needs to be made the case must be discussed with the radiologist to determine if substitution is possible. If not, subsequent objective statuses are indeterminate.

Target disease

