5.2.10. Adequate Baseline Tumor Assessment

Adequate baseline is defined using the following criteria:

- All baseline assessments must be within 42 days prior to and including the first dose of study treatment.
- All documented lesions must have non-missing assessments (ie, non-missing measurements for target lesions and non-missing lesion status at baseline for non-target lesions).

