6.2.2.1. Objective Response as Assessed by the Investigator per RECIST v1.1

The following analyses will be based on the FAS by treatment group. Assessment of response will be made using RECIST v1.1.

Best Overall Response (BOR) will be assessed based on reported overall lesion responses at different evaluation time points from the first dose of study treatment until the first documentation of PD, according to the following rules:

- CR = at least two determinations of CR at least 4 weeks apart and before first documentation of PD.
- PR = at least two determinations of PR or better at least 4 weeks apart and before first documentation of PD (and not qualifying for a CR).
- SD (applicable only to patients with measurable disease at baseline) = at least one SD assessment (or better) ≥ 6 weeks after the first dose of study treatment and before first documentation of PD (and not qualifying for CR or PR).
- Non-CR/non-PD (applicable only to patients with non-measurable disease at baseline) = at least one non-CR/non-PD assessment (or better) ≥ 6 weeks after the first dose of study treatment and before first documentation of PD (and not qualifying for CR or PR).

- PD = progression \leq 12 weeks after the first dose of study treatment (and not qualifying for CR, PR, SD or non-CR/non-PD).
- NE: all other cases.

Only tumor assessments performed on or before the start of any further anti-cancer therapies will be considered in the assessment of BOR. Clinical deterioration will not be considered as documentation of disease progression.

Objective Response (OR) is defined as BOR of CR or PR according to RECIST v1.1

Patients who do not have a post-baseline radiographic tumor assessment (including due to early clinical progression), who receive anti-cancer therapies other than the study treatments prior to reaching a CR or PR, or who die, progress, or drop out for any reason prior to reaching a CR or PR will be counted as non-responders in the assessment of OR. Each patient will have an objective response status (0: no OR; 1: OR). OR rate (ORR) is the proportion of patients with OR in the analysis set.

ORR by treatment group will also be calculated along with the 2-sided 95% CI using the Clopper-Pearson method (exact CI for a binomial proportion as computed by default by the FREQ procedure using the EXACT option).

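### A baseline scan 29 to 35 days before first dose satisfies the visit schedule and the SAP, but Appendix 2 calls it inadequate and steers the investigator towards indeterminate RECIST 1.1 statuses.

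*Protocol*

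**What the plan says.** Three places set a time limit on the same baseline scan.

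- **Schedule.** Protocol Table 1 lists the baseline CT or MRI under Screening. Footnote 1 says of screening "To be obtained within 28 days prior to registration", and Section 6.1 agrees: "Screening is to be performed within 28 days of registration". Footnote 18 and Section 7.2, which cover tumor assessments, give no separate baseline window. On dosing, footnote 15 says "Study treatments administration should begin within 7 days of registration" and Section 5.4 says "Study treatment administration should start no later than 7 days after registration".
- **Appendix 2 (RECIST 1.1).** "For an adequate baseline assessment, all required scans must be done within 28 days prior to treatment and all disease must be documented appropriately". The consequence follows: "If baseline assessment is inadequate, subsequent statuses generally should be indeterminate".
- **SAP 5.2.10.** "All baseline assessments must be within 42 days prior to and including the first dose of study treatment".

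SAP 6.2.2.1, whose heading names the investigator as assessor, says best overall response (BOR) is "assessed based on reported overall lesion responses at different evaluation time points from the first dose of study treatment". No section says which of the three limits governs the status the investigator enters.

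**The concern.** The schedule counts from registration, while Appendix 2 counts from treatment. Because dosing may come a week after registration, a site can follow the schedule exactly and still hold a baseline scan that Appendix 2 calls inadequate. Appendix 2 is the text an investigator uses to score RECIST 1.1 response.

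Two identical patients could then be scored differently. One investigator relies on the schedule and reports a partial response. Another applies Appendix 2 and reports indeterminate. The second patient counts as a non-responder in the objective response rate (ORR), does not enter duration of response or time to response and, in an expansion cohort, can lose all PFS follow-up. The difference would come from which page the site read, not from the drug.

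**Working it through.** The plan states no figure to reproduce here. The check is calendar arithmetic, then tracing the consequence through the SAP.

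**Inputs**
- Scan to registration: up to 28 days (Table 1 footnote 1; Section 6.1).
- Registration to first dose: up to 7 days (footnote 15; Section 5.4).
- Appendix 2 limit: 28 days before treatment.
- SAP 5.2.10 limit: 42 days before first dose.

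**Step 1: longest compliant interval.** 28 + 7 = 35 days from scan to first dose.

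**Step 2: the three rules side by side**

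| Scan age at first dose | Schedule (28 + 7) | Appendix 2 | SAP 5.2.10 |
|---|---|---|---|
| 0–28 days | can comply | adequate | adequate |
| 29–35 days | can comply | inadequate | adequate |
| 36–42 days | outside | inadequate | adequate |

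For example, a scan 26 days before registration with dosing 6 days after it is 26 + 6 = 32 days old, in the middle row.

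**Step 3: what an indeterminate entry does.** The SAP's baseline test passes this patient, but it does not alter the status the investigator reported.
- *Response.* If every post-baseline status is indeterminate, none of the named BOR categories is met. BOR is NE, and the patient is a non-responder in ORR (SAP 6.2.2.1).
- *PFS, expansion cohorts only.* An indeterminate visit is not an adequate post-baseline assessment (SAP 5.2.11). With none adequate, PFS is censored at first dose. Under SAP Table 3, PD or death still counts as an event if it falls within 16 weeks of first dose or follows at most one inadequate assessment.

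**Step 4: how many patients.** The documents give no distribution of scan-to-dose intervals, so this is an illustration only. Assume the scan falls uniformly 0–28 days before registration (U) and dosing uniformly 0–7 days after it (V), independently. Then P(U + V > 28) = E[V]/28 = 3.5/28 = 12.5%. If dosing always falls within 3 days, it is 1.5/28 = 5.4%. In 40 expansion patients that is 40 × 0.125 = 5, or 40 × 0.054 = about 2, with a scan in the disputed band. Each responder lost from a group of 40 moves ORR by 1/40 = 2.5 percentage points.

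**The case against.** The strongest reply is that a site can satisfy every rule at once. The windows are nested: a scan within 28 days of dosing meets all three, and Appendix 2 also asks for baseline imaging as near to study start as possible. That is correct. A reader might infer that the three windows are incompatible, but they are not; the conflict is confined to the 29–35 day band, and Appendix 2 is the outlier.

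A reader might also infer that every later response of such a patient becomes indeterminate. The documents do not support that. Appendix 2 says this is generally so, which leaves discretion. Under its Table 11, target progression, non-target progression or a new lesion still gives PD. The irRECIST rules in Appendix 3 contain no 28-day requirement. What remains is that CR, PR and SD can be lost while progression stays reportable, so any effect on RECIST 1.1 ORR is downward.

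A third inference is that the SAP's 42 days is wrong and should be cut to 35. Protocol Section 9 lets the SAP modify planned analyses, and 42 days already covers the 28 + 7 schedule. A cut would make patients with scans 36–42 days old inadequate at baseline. Table 1 also carries a minus-7-day visit window in its screening column. If that extends screening, the longest compliant interval is 28 + 7 + 7 = 42 days, exactly the SAP limit. The public copy of the table does not settle this, so 35 days is not established as the ceiling.

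Finally, efficacy here is secondary and descriptive, and no hypothesis is tested. That limits the harm but does not remove the inconsistency.

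**Conclusion.** The point holds in this limited form. A scan 29–35 days before first dose complies with the schedule, is adequate in the SAP and is inadequate in Appendix 2. Because BOR rests on reported statuses, the SAP's wider window cannot undo an indeterminate entry. A compliant patient's CR, PR or SD can become NE, and in the expansion cohorts PFS can be censored at first dose, depending on how the site reads Appendix 2.

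The size is unknown. The 5.4% to 12.5% range rests wholly on the uniform-timing assumptions and would be smaller if sites scan close to dosing. It counts patients exposed to the conflict, not responses lost. If Table 1's minus-7-day entry extends screening, the disputed band widens to 29–42 days. The DLT primary endpoint, the MTD estimate and the irRECIST analyses are not affected.

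**What to change.** 1. Amend the Appendix 2 sentence so that a baseline is adequate in timing when the scans meet the Table 1 screening window: within 28 days before registration, with first dose within 7 days of registration. Keep the requirement that all disease be documented.
2. State in Table 1 whether the minus-7-day entry in the screening column extends that window, and word Appendix 2 to match.
3. Leave SAP 5.2.10 at 42 days. It covers the 28 + 7 schedule and also 28 + 7 + 7.

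The cost is a wording change in the protocol. It needs no extra scans, no change to the SAP and no change to the sample size. For patients already enrolled, the recorded scan and first-dose dates would show how many fall in the band and whether any were reported as indeterminate for that reason.
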